
 
To compare the wound infection incidence between both treatment groups.
 
	
 
Wound infection incidence assessed at the Day 10, Month 1, and Month 3 visits or at the Early Discontinuation visit (diagnosed according to the Centers for Disease Control and Prevention [CDC] criteria for surgical site infection [Section 15.1]).
 
Wound infection assessed on a binary scale (“1 - yes” or “0 - no”) for the following criteria: 
 
Presence of erythema
 
Presence of edema
 
Presence of pain at rest
 
Presence of elevated temperature
 
 A total score will be calculated for each subject.
 

 
To evaluate the investigator satisfaction with the cosmetic outcome after the closure of the target surgical incision/laceration with MAR-CUTIS versus Dermabond Advanced.
 
	
 
Investigator-completed POSAS done at the Month 1 and Month 3 visits or at the Early Discontinuation visit (if Early Discontinuation occurs before Month 1).
 

	

Investigator-completed Modified Hollander Cosmesis Scale (mHCS) done at the Day 10 and Month 1 visits or at the Early Discontinuation visit (if Early Discontinuation occurs before Month 1).

To evaluate the subject comfort with the device during and after treatment with MAR-CUTIS versus Dermabond Advanced.

	

A questionnaire related to subject experience and satisfaction with the device completed by the subject at the Day 10 and Month 1 visits or at the Early Discontinuation visit (if Early Discontinuation occurs before Month 1).

A subject-related questionnaire completed by the investigator at the Day 0 and Month 1 visits or at the Early Discontinuation visit (if Early Discontinuation occurs before Month 1).

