## 7.2 Discussion of Study Design

### 7.2.1 Study Design

The study will include 3 levels of stratification:

- By wound type (lacerations and incisions): approximately 40 subjects with lacerations will be randomized.
- By skin type according to the Fitzpatrick classification (types I to III versus types IV to VI): approximately 40 subjects with skin types IV to VI will be randomized; approximately 20 subjects from this cohort will have skin types V to VI.
- By age group (2 to 21 years of age and  $\geq 22$  years of age): approximately 30 subjects in the 2 to 21 age group will be randomized. To ensure that the pediatric population is not dominated by an adolescent sub-group, approximately 5 subjects aged 15 to  $< 22$  years will be included.

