### 9.3.6 Other Safety Assessments

Wound infection incidence, diagnosed according to the CDC criteria for surgical site infection, will be assessed by an investigator at the Day 10, Month 1, Month 3/Early Discontinuation, and any unscheduled study visits. In addition, the infection will be assessed on a binary scale (“1 - yes” or “0 - no”) for the criteria below. A total score will be generated for each subject.

- Presence of erythema
- Presence of edema
- Presence of pain at rest
- Presence of elevated temperature

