## **15 APPENDICES**

### 15.1 Centers for Disease Control and Prevention Surgical Site Infection Criteria

Criterion	Surgical Site Infection (SSI)
	
Superficial incisional SSI Must meet the following criteria:
 
Date of event for infection occurs within 30 days after any NHSN operative procedure (where day 1 = the procedure date) AND involves only skin and subcutaneous tissue of the incision AND patient has at least one of the following:
 
 
a. purulent drainage from the superficial incision.
 
b. organisms identified from an aseptically-obtained specimen from the superficial incision or subcutaneous tissue by a culture or non-culture based microbiologic testing method which is performed for purposes of clinical diagnosis or treatment (for example, not Active Surveillance Culture/Testing (ASC/AST).
 
c. superficial incision that is deliberately opened by a surgeon, attending physician** or other designee and culture or non-culture based testing is not performed.
 
 
AND patient has at least one of the following signs or symptoms: pain or tenderness; localized swelling; erythema; or heat.
 
 
d. diagnosis of a superficial incisional SSI by the surgeon or attending physician** or other designee.
 
 
www.cdc.gov/nhsn/xls/icd10-pcs-pcm-nhsn-opc.xlsx www.cdc.gov/nhsn/xls/cpt-pcm-nhsn.xlsx
 
** The term attending physician for the purposes of application of the NHSN SSI criteria may be interpreted to mean the surgeon(s), infectious disease, other physician on the case, emergency physician or physician's designee (nurse practitioner or physician's assistant).

Comments
	
There are two specific types of superficial incisional SSIs:
 
 
1. Superficial Incisional Primary (SIP) – a superficial incisional SSI that is identified in the primary incision in a patient that has had an operation with one or more incisions (for example, C-section incision or chest incision for CBGB)
 
2. Superficial Incisional Secondary (SIS) – a superficial incisional SSI that is identified in the secondary incision in a patient that has had an operation with more than one incision (for example, donor site incision for CBGB)
 

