	
Deep incisional SSI Must meet the following criteria: The date of event for infection occurs within 30 or 90 days after the NHSN operative procedure (where day 1 = the procedure date) according to the list in Table 2 AND involves deep soft tissues of the incision (for example, fascial and muscle layers) AND patient has at least one of the following:
 
 
a. purulent drainage from the deep incision.
 
b. a deep incision that spontaneously dehisces, or is deliberately opened or aspirated by a surgeon, attending physician** or other designee
 
 
AND
 
organism is identified by a culture or non-culture based microbiologic testing method which is performed for purposes of clinical diagnosis or treatment (for example, not Active Surveillance Culture/Testing (ASC/AST) or culture or non-culture based microbiologic testing method is not performed
 
AND
 
patient has at least one of the following signs or symptoms: fever (>38°C); localized pain or tenderness. A culture or non-culture based test that has a negative finding does not meet this criterion.
 
 
c. an abscess or other evidence of infection involving the deep incision that is detected on gross anatomical or histopathologic exam, or imaging test.
 
 
** The term attending physician for the purposes of application of the NHSN SSI criteria may be interpreted to mean the surgeon(s), infectious disease, other physician on the case, emergency physician or physician's designee (nurse practitioner or physician's assistant).

Comments
	
There are two specific types of deep incisional SSIs:
 
 
1. Deep Incisional Primary (DIP) – a deep incisional SSI that is identified in a primary incision in a patient that has had an operation with one or more incisions (for example, C-section incision or chest incision for CBGB)
 
2. Deep Incisional Secondary (DIS) – a deep incisional SSI that is identified in the secondary incision in a patient that has had an operation with more than one incision (for example, donor site incision for CBGB)
 

---

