FX	Open reduction of fracture		
HER	Herniorrhaphy		
HPRO	Hip prosthesis		
KPRO	Knee prosthesis		
PACE	Pacemaker surgery		
PVBY	Peripheral vascular bypass surgery		
VSHN	Ventricular shunt		

Note: Superficial incisional SSIs are only followed for a 30-day period for all procedure types.

Secondary incisional SSIs are only followed for a 30-day period regardless of the surveillance period for the primary site.

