13.2.3 Wound infection

Wound infection evaluation, diagnosed according to the CDC criteria for surgical site infection, will be assessed by a treating physician and recorded in the e-CRF.

13.2.3.1 Wound infection incidence at Day 10, Month 1 and Month 3

Wound infection incidence, evaluated through the presence of erythema, edema, pain at rest or elevated temperature, will be summarized with descriptive statistics at the Day 10, Month 1, and Month 3 study visits.

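### Wound infection has two incompatible case definitions; the CDC one lists no category for lacerations and stops at 30 days for superficial infection, although follow-up runs to Month 3

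*Protocol*

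**What the plan says.** Protocol section 6 sets a secondary objective of comparing wound infection between arms, with "Wound infection incidence assessed at the Day 10, Month 1, and Month 3 visits or at the Early Discontinuation visit". Section 9.3.6 repeats that infection is "diagnosed according to the CDC criteria for surgical site infection, will be assessed by an investigator at the Day 10, Month 1, Month 3/Early Discontinuation"; unscheduled visits are included too. SAP 13.2.3 opens in the same way: "Wound infection evaluation, diagnosed according to the CDC criteria for surgical site infection, will be assessed by a treating physician". None of these texts separates incisions from lacerations, although section 7.2.1 plans for both: "By wound type (lacerations and incisions): approximately 40 subjects with lacerations will be randomized".

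Appendix 15.1 supplies the criteria. Superficial infection carries the condition "Date of event for infection occurs within 30 days after any NHSN operative procedure (where day 1 = the procedure date"), and the note to Table 2 says "Superficial incisional SSIs are only followed for a 30-day period for all procedure types". Deep infection carries the condition "The date of event for infection occurs within 30 or 90 days after the NHSN operative procedure", with the period set by Table 2. Organ/space infection is worded in the same way. Table 2 puts abdominal hysterectomy and exploratory laparotomy under 30 days and herniorrhaphy under 90 days. It has no entry for repair of a laceration.

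Two other texts use a different approach. SAP 13.2.3.1 tabulates infection incidence at Day 10, Month 1 and Month 3 through four local signs (redness, swelling, pain at rest, raised temperature). SAP 13.2.3.2 sums the same four signs into a score and sets a sign to 0 when it is unrecorded or missing. Protocol 8.2.2 to 8.2.4, however, make the infection evaluation and its score conditional on an infection having occurred.

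**The concern.** The documents do not settle what makes a subject an infection case. A site that follows Appendix 15.1 literally has no listed category for a laceration and no way to class a new superficial infection after day 30 as a case. The superficial layer is the one the adhesive closes. A programmer who follows SAP 13.2.3.1 would count any wound with one local sign at any visit. The two rules give different numerators from the same subjects.

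The stake is how the infection tables are read. Infection is the first predictable adverse event that the Introduction lists for skin adhesives (3.6%). Under the CDC rule, a table with no late superficial infection, or none in lacerations, would partly reflect the definition and not the devices. Under the four-sign rule, ordinary post-operative redness or swelling could be reported as infection.

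**Working it through.** The plan states no figure for this endpoint that could be reproduced. The check is a day count, a share, and a comparison of the rules.

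**Inputs.** Month 1 window ±7 days and Month 3 window ±14 days (protocol 7.1.2); 1 month = 30 days (SAP 16.1.1.9); procedure date = CDC day 1 (Appendix 15.1) = protocol Day 0; 189 subjects (7.3.1); about 40 lacerations (7.2.1) or 15% lacerations (10.2); 3.6% infection with adhesives (section 5).

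**Time limits.**
- CDC day 30 = protocol Day 29, and CDC day 90 = protocol Day 89.
- Month 1 visit: 30 ± 7 = Days 23 to 37, so it can fall up to 8 days after the superficial limit.
- Month 3 visit: 90 ± 14 = Days 76 to 104, entirely after the superficial limit. The limit applies to the date of the event. A Month 3 visit could therefore add a superficial CDC case only if onset was by Day 29 and had not been recorded earlier, for instance after a Month 1 visit on Day 23.
- Nominal follow-up is Days 0 to 90 = 91 days, of which Days 0 to 29 = 30 days are countable. The share not countable is 61/91 = 67%. With Month 3 at Day 76 it is 1 − 30/77 = 61%; with Month 3 at Day 104 it is 1 − 30/105 = 71%.
- Deep infection after abdominal hysterectomy or exploratory laparotomy also ends at Day 29. Among the eligible procedures only hernia repair clearly has 90 days, and Day 89 falls inside the Month 3 window.

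**Lacerations.** By the stratification target, 40/189 = 21.2%. By the sample-size assumption, 0.15 × 189 = 28.35, about 28 subjects (15%).

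**Illustrative size.** Assume 3.6% in both wound types and no laceration counted. The overall rate becomes 3.6% × (1 − 0.212) = 2.84%, or 3.6% × 0.85 = 3.06%. Expected cases lost are 0.036 × 40 = 1.4, or 0.036 × 28.35 = 1.0, out of 0.036 × 189 = 6.8.

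**The rules side by side.**

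| Example | CDC criteria (Appendix 15.1) | Four signs (SAP 13.2.3.1) |
|---|---|---|
| Laceration with purulent drainage and redness, Day 10 | No listed procedure category | Case |
| Hysterectomy incision, superficial infection with redness and onset Day 60 | Not a case (past 30 days) | Case if the redness is recorded at a scheduled visit |
| Incision with redness and warmth only, Day 10 | Does not meet criterion d by itself | Case |
| Incision with purulent drainage but none of the four signs, Day 10 | Case (criterion a) | Not a case |

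The rules disagree in both directions. Protocol 8.2 adds a third layer. If the site decides that no infection occurred, whether because CDC is not met or for another reason, the signs may not be collected, and SAP 13.2.3.2 then scores them 0. The score can thus inherit the CDC exclusions without showing them as missing.

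**The case against.** The strongest reply is that Appendix 15.1 is not the only standard. The SAP subsections that build the tables use four signs with no procedure condition and no time limit, so a laceration or a Month 3 infection can be tabulated. That is correct. A reader might infer from the appendix alone that such infections can never count and that incidence is near zero by definition; the documents do not support that. The four-sign rule still does not rescue the endpoint. SAP 13.2.3 keeps the CDC diagnosis as its opening requirement, the visit lists make collection conditional, missing signs become 0, and Appendix 15.1 says that redness, warmth and swelling alone do not satisfy criterion d.

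Second, the exclusion of lacerations is inferred. The superficial criterion speaks of any NHSN operative procedure without pointing to Table 2, that table covers selected categories, and the full code lists are only linked. This stands. The documents show that no listed category fits; they do not show that no code exists. The appendix's statement that an infected localized stab wound is not a surgical site infection points the same way but is not about lacerations.

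Third, adverse events are recorded to the last visit (protocol 9.3.2.1), so infections of either wound type at any time can appear there. This is a real but partial mitigation, because the adverse event tables do not supply the planned infection endpoint.

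Fourth, the endpoint is descriptive and the expected loss is 1.0 to 1.4 cases. This also stands, and it limits the weight of any argument about a diluted difference between arms. Protocol 10.1.4 promises safety summaries within the randomization strata, which include wound type, but it names only adverse events as safety endpoints.

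**Conclusion.** The point holds as a conflict of definitions. The 30-day stop for superficial infection is explicit, and it makes 61% to 71% of nominal follow-up non-countable for new superficial CDC cases, including the whole Month 3 window. The lack of a category for lacerations concerns 15% to 21% of subjects and is a strong inference, subject to code lists that the documents do not include. The four-sign rule has neither limit but is non-specific and conflicts with the CDC diagnosis required in the same SAP section.

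Depending on which rule is applied, incidence is under-counted in lacerations and after day 30, or over-counted through non-specific signs. The fall from 3.6% to between 2.8% and 3.1% is illustrative only: it assumes equal rates in both wound types and that no laceration is counted. It would be wrong to conclude that late or laceration infections go unreported in the trial, since they can be recorded as adverse events. The primary endpoint, its power and the noninferiority conclusion are untouched. The change should be made, but the trial does not depend on it.

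**What to change.** In protocol 9.3 and 9.3.6 and SAP 13.2.3:

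- Use one case definition for every target wound: the clinical elements of the CDC superficial or deep criteria, timed from adhesive application to Month 3, without the NHSN-procedure condition.
- Report formal CDC surgical site infection separately, with incisions only as the denominator and within its own 30- or 90-day windows.
- Keep the four-sign score as a separate descriptive variable recorded for all subjects at each infection visit. Remove the condition in protocol 8.2.2 to 8.2.4 that an infection must have occurred, and do not label the signs infection incidence in SAP 13.2.3.1.
- Show all of these by wound type.

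The cost is protocol and SAP wording, a few extra table rows, and entry of the four signs for every subject. No new visits or examinations are needed, since the schedule already evaluates wound infection at Day 10, Month 1, Month 3 and Early Discontinuation. The downside is that the laceration and late-infection rows will not be formal CDC rates and should be labelled accordingly.

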**Table 3. Specific Sites of an Organ/Space SSI.**

Code	Site	Code	Site
BONE	Osteomyelitis	MED	Mediastinitis
BRST	Breast abscess or mastitis	MEN	Meningitis or ventriculitis
CARD	Myocarditis or pericarditis	ORAL	Oral cavity (mouth, tongue, or gums)
DISC	Disc space	OREP	Other infections of the male or female reproductive tract
EAR	Ear, mastoid	PJI	Periprosthetic Joint Infection
EMET	Endometritis	SA	Spinal abscess without meningitis
ENDO	Endocarditis	SINU	Sinusitis
GIT	GI tract	UR	Upper respiratory tract
IAB	Intraabdominal, not specified	USI	Urinary System Infection
IC	Intracranial, brain abscess or dura	VASC	Arterial or venous infection
JNT	Joint or Bursa	VCUF	Vaginal cuff
LUNG	Other infections of the lower respiratory tract		

---

## 15.2 Dermabond Advanced Instructions for Use

## INSTRUCTIONS FOR USE

### TOPICAL SKIN ADHESIVE (2-Octyl Cyanoacrylate)

#### DESCRIPTION

DERMABOND ADVANCED™ Topical Skin Adhesive is a sterile, liquid topical skin adhesive containing a monomeric (2-octyl cyanoacrylate) formulation and the colorant D & C Violet #2. It is provided as a single-use applicator in a blister package. The pen style applicator is composed of a crushable ampoule contained within a plastic applicator. As it is applied to the skin, the liquid is syrup-like in viscosity and polymerizes within minutes. Studies have shown that following application, DERMABOND ADVANCED™ Adhesive acts as a barrier to prevent microbial penetration as long as the adhesive remains. See DIRECTIONS FOR USE.

#### INDICATIONS

DERMABOND ADVANCED™ Adhesive is intended for topical application only, to hold closed easily approximated skin edges of wounds from surgical incisions, including incisions from minimally invasive surgery, and simple, thoroughly cleansed, trauma-induced lacerations. DERMABOND ADVANCED™ Adhesive may be used in conjunction with, but not in place of, deep dermal stitches.

#### CONTRAINDICATIONS

- Do not use on any wound with evidence of active infection, gangrene, or wounds of decubitus etiology.
- Do not use on mucosal surfaces or across mucocutaneous junctions (e.g., oral cavity, lips), or on skin which may be regularly exposed to body fluids or with dense natural hair.
- Do not use on patients with a known hypersensitivity to cyanoacrylate or formaldehyde.

#### WARNINGS

- DERMABOND ADVANCED™ Adhesive is a fast setting adhesive capable of adhering to most body tissue and many other materials, such as surgical gloves and stainless steel. Inadvertent contact with any body tissue, and any surfaces or equipment that are not disposable or that cannot be readily cleaned with a solvent such as acetone should be avoided.
- Polymerization of DERMABOND ADVANCED™ Adhesive may be accelerated by water or fluids containing alcohol. DERMABOND ADVANCED™ Adhesive should not be applied to wet wounds.
- DERMABOND ADVANCED™ Adhesive should not be applied to the eye. If contact with the eye occurs, flush the eye copiously with saline or water. If residual adhesive remains, apply topical ophthalmic ointment to help loosen the bond and contact an ophthalmologist.
- When closing facial wounds near the eye with DERMABOND ADVANCED™ Adhesive, position the patient so that any runoff of adhesive is away from the eye. The eye should be closed and protected with gauze. Prophylactic placement of petroleum jelly around the eye, to act as a mechanical barrier or dam, can be effective in preventing inadvertent flow of adhesive into the eye. DERMABOND ADVANCED™ Adhesive will not adhere to skin pre-coated with petroleum jelly. Therefore, avoid using petroleum jelly on any skin area where DERMABOND ADVANCED™ Adhesive is intended to adhere.
- DERMABOND ADVANCED™ Adhesive should not be used below the skin because the polymerized material is not absorbed by tissue and can elicit a foreign body reaction. Avoid excessive pressure of the applicator tip against wound edges or surrounding skin. This can force the wound edges apart and allow adhesive into the wound. DERMABOND ADVANCED™ Adhesive should be applied with a light brushing motion of the applicator tip over easily approximated wound edges.
- DERMABOND ADVANCED™ Adhesive should not be used in areas of high skin tension or across areas in which tension may increase, such as knuckles, elbows, or knees, unless the joint will be immobilized during the skin healing period or unless skin tension has been removed by application of another wound closure device (e.g., sutures or skin staples) prior to application of DERMABOND ADVANCED™ Adhesive.
- As with all wounds, DERMABOND ADVANCED™ Adhesive treated wounds should be monitored for signs of infection. Wounds with signs of infection, such as erythema, edema, warmth, pain, and purulent exudate, should be evaluated and treated according to standard practice for infection.
- DERMABOND ADVANCED™ Adhesive should not be used on wound sites that will be subjected to repeated or prolonged moisture or friction.

- DERMABOND ADVANCED™ Adhesive should only be used after wounds have been thoroughly and adequately cleaned and debrided in accordance with standard surgical practice.
- DERMABOND ADVANCED™ Adhesive polymerizes through an exothermic reaction in which a small amount of heat is released sometimes resulting in a sensation of warmth. Applying DERMABOND ADVANCED™ Adhesive in one continuous layer onto a dry wound and allowing time for polymerization, will minimize the warm sensation.
- DERMABOND ADVANCED™ Adhesive is packaged for single patient use. Discard remaining opened material after each wound closure procedure.
- Do not resterilize DERMABOND ADVANCED™ Adhesive.
- Do not place DERMABOND ADVANCED™ Adhesive in a procedure pack/tray that will be sterilized prior to use. Exposure of DERMABOND ADVANCED™ Adhesive, to excessive heat (as in autoclaves or ethylene oxide sterilization) or radiation (such as gamma or electron beam) will increase its viscosity and may render the product unusable.

### PRECAUTIONS

- Do not apply liquid or ointment medications or other substances to the wound after closure with DERMABOND ADVANCED™ Adhesive, as these substances can weaken the polymerized film and allow for skin edge separation. Prior to application, cleanse the application site thoroughly to remove any remaining topical medications/anesthetics.
- DERMABOND ADVANCED™ Adhesive, as a liquid, is syruplike in viscosity. To prevent inadvertent flow of liquid DERMABOND ADVANCED™ Adhesive to unintended areas, the wound should be maintained in a horizontal position, with DERMABOND ADVANCED™ Adhesive applied from above.
- DERMABOND ADVANCED™ Adhesive should be used immediately after crushing ampoule because the adhesive will polymerize in the applicator, rendering the device unusable.
- If unintended bonding of intact skin occurs, peel the adhesive from the skin, but do not pull the skin edges apart. Petroleum jelly or acetone may help loosen the bond. Other agents such as water, saline, or soap are not expected to immediately loosen the bond.

